The RELIEF™ Ureteral Stent – Assessment of Retrograde Urinary Reflux and Distal Coil Bladder Position

NCT03266770

11/29/2021

Objectives

Primary Objectives:

• Evaluation of the stent placement and the adequacy of short term drainage (defined as the presence of the stent in the ureter and the lack of surgical or other intervention to treat symptoms associated with the stent itself on the stented side during the first 48 hours).

Secondary Objectives:

- Assessment of retrograde urine reflux after placement of the RELIEF® Ureteral Stent using cystography after contrast gravity-filling of the bladder and assigning a urinary reflux grade based on:
 - o Grade I: urine refluxes into the ureter only.
 - o Grade II: urine refluxes into the ureter and up to the kidney without dilation.
 - o Grade III: urine refluxes into the ureter and kidney and causes mild dilation.
 - Grade IV: urine refluxes into ureter and kidney and causes dilation without twisting of the ureter.
 - Grade V: urine refluxes into ureter and kidney and causes significant dilation with twisting of the ureter.
- Visualization of distal coil in bladder, after RELIEF Stent placement. Document placement using a cystoscope and obtain image, if possible.
- Assessment of adverse events (incidence, relationship to device, severity) attributed to the
 Ureteral Stent, compared to established adverse event rates from published clinical studies and
 FDA reportable event occurrences, compared to number of US annual ureteral stent
 placements.
- Reporting the Ureteral Stent Symptoms Questionnaire before stent placement, after placement and prior to removal.

Background

[figure not shown]
Traditional ureteral stents are commonly used in practice to relieve renal obstruction or as a scaffold to promote healing after endoscopic or open/laparoscopic surgeries involving the ureter [1]. However, there are a lot of morbidities that can be associated with placing these stents either due to irritation of the bladder or affection the kidney.

The most commonly reported symptoms include urgency, urinary frequency, dysuria, incontinence, hematuria, suprapubic discomfort, fever due to urinary tract infections and flank pain and they can occur in up to 80% of stented patients. Sometimes, the symptoms are poorly tolerated and can negatively affect the patient quality of life [2, 3].

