All subjects should be familiar with the Informed Consent and its content, and have been given opportunity to have their questions answered about the study prior to signing the Informed Consent. At the time of admission, the patient will be assessed for suitability. If the patient meets the inclusion/exclusion criteria, he/she will enter the study.

Results will be shared with ONLY the research participants' doctors who are among the approved study team by the UH IRB.

Study Design

Allocation: Non-randomized

Endpoint Classification: Safety/Efficacy Study

Intervention Model: Single Group Assignment

Masking: Open Label

Primary Purpose: Treatment

Study Procedures

Informed Consent: Eligible subjects will be consented by a Research Nurse or Investigator prior to the procedure.

Inclusion Criteria: Confirmation of fulfilling Inclusion criteria (e.g., consent, examination, indication) and that subject does not have any Exclusion criteria.

Pre-Stenting Evaluation (Day 0 or within 24 hours of Day 0): USSQSurvey and 10 -Point Pain Score: Subject completesUSSQsurvey for baseline evaluation (pre-stenting, Day 0)

Ureteral Stenting Procedure (Day 0):

Pre-stent cystogram

- Instill dye (up to 300 cc) under gravity-filling cystogram for assessment of pre-stent reflux and capture Xray image (with C-arm). (Exclude patients with reflux). Cystogram image will be saved.
- Drain bladder

[CRF: Pre-Stent Reflux Result; Pre-Stent Cystogram Image]

Ureteral Stent Placement

- Obtain retrograde pyelogram.
- Insert guidewire and perform ureteroscopy for treatment when needed. (Based on the urologist's discretion, if trauma has been induced to the distal ureter due to ureteroscopy maneuvers, these patients will be excluded).

- Any remaining contrastshould be flushed by irrigation ofsaline. Confirmatory X-ray image may be captured to ensure that contrast has been adequately removed (Note: If residual contrast considered not acceptable or confirmatory X-ray not recommended, subject may be excluded from study and traditional stent used).
- Remove the pull-outsuture, then place RELIEF stent under cystoscopy. Stent with pusher placed over guidewire and inserted. Position pusher until reach 4 cm mark. Remove wire. Back-out pusher. Confirm xray image ofstent position and save the image.

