- Study success defined as adequate short term drainage defined as the presence of the stent in the ureter and the lack of surgical or other intervention to treat symptoms associated with the stent itself or failure of the stent on the stented side during the first 48 hours [Day 0-2] following placement. [Note: In some cases, the ureteral stent may not be sufficient to relieve pain (not associated with stent specifically) and alternative surgical treatment may be warranted. In these cases, patient data will be captured but non-device related cause captured as reason for subject stenting termination.]
- Assessment of retrograde urine reflux after placement of the RELIEF® Ureteral Stent, as determined by the visualization of urine in the distal ureter to the kidney using cystography after contrast gravity-filling of the bladder and assigning a urinary reflux grade based on:
 - Grade I: urine refluxes into the ureter only.
 - Grade II: urine refluxes into the ureter and up to the kidney without dilation.
 - Grade III: urine refluxes into the ureter and kidney and causes mild dilation.
 - Grade IV: urine refluxes into ureter and kidney and causes dilation without twisting of the ureter.
 - Grade V: urine refluxes into ureter and kidney and causes significant dilation with twisting of the ureter.

• Visualization of distal coil in bladder, after RELIEF Stent placement. Document placement using a cystoscope.

2- Primary safety endpoint:

• Assessment of adverse events (incidence, relationship to device, severity) attributed to the Ureteral Stent, compared to established adverse event rates from published clinical studies and FDA reportable event occurrences, compared to number of US annual ureteral stent placements. (No anticipated adverse events from Stent design; known complications from stenting may be observed.)

3- Secondary endpoint:

• USSQ Scale (Ureteral Stent Symptoms Questionnaire) [Time Frame: Day 0 (pre-stenting), 24-48 hours post-stent placement, and Day 7-30 prior to stent removal].

Stopping Rules: In the occurrence of any unexpected adverse events to the participants, the study team will hold study recruitment until the investigation is completed. Patients who experience unanticipated adverse events will have the RELIEF stent promptly removed.

Expected Adverse Events include:

- Flank pain/loin discomfort
- Flank pain when voiding
- Suprapubic pain/lower abdominal pain
- Trigonal irritation
- Urinary frequency
- Nocturia
- Urinary urgency

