The study will pay for all procedures/devices that are directly associated with this research study. This includes the RELIEF stent, and the extra x-rays. Procedures or drugs that are considered standard of care will be the responsibility of the patient or his/her insurance company

Research Participant Compensation

No compensation will be provided to study participants.

[figure not shown]
Provisions to Monitor the Data to Ensure the Safety of Research Participants

The group of investigators, including the principal investigator, and the research support staff (nurses, CMA's, data managers, and regulatory) will carry out the Data and Safety Monitoring Plan. Data will be reviewed quarterly to ensure that it is accurate, complete, and that its collection is in compliance with the protocol. There will also be a continual assessment of the risks and benefits.

Furthermore, Case report forms will be generated for each subject and completed by the investigator or study coordinator. The investigator or study coordinator will countersign each form. After the case report forms for a visit are completed, the research coordinator will enter a limited set of data into a data management system. Original case report forms will be securely maintained at the clinical sites. Completed copies of the case report forms will be sent to the research coordinator where they will be stored on the Shared "S" Drive. Subjects will be asked to report any adverse events to the study coordinator or physician. All adverse events will be reported on a standardized form that will elicit the number and specify the type of tests used, therapy (or therapies) used, and clinical visits (office, ER and hospitalization) required until the event is resolved.

[figure not shown]
DEVICE DESCRIPTION:

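### The primary safety endpoint summarises stent-attributed events but does not require the published rates it is compared with to use the same attribution rule, which favours the device wherever a published rate is all-cause

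*Protocol*

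**What the plan says.** The Study Endpoints section of the protocol, under the primary safety endpoint, calls for "Assessment of adverse events (incidence, relationship to device, severity) attributed to the Ureteral Stent". The Secondary Objectives use the same wording. These events are to be "compared to established adverse event rates from published clinical studies and FDA reportable event occurrences, compared to number of US annual ureteral stent placements". A bracketed remark in the endpoint adds: "No anticipated adverse events from Stent design; known complications from stenting may be observed".

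Other parts of the protocol bear on how this endpoint works:

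- Study Design: "Intervention Model: Single Group Assignment" and "Masking: Open Label". There is no concurrent control, so every comparison is external.
- Provisions to Monitor the Data: safety monitoring is carried out by "The group of investigators, including the principal investigator, and the research support staff", and the investigator or coordinator completes the case report forms. No causality criteria and no independent reviewer are described.
- The same section: "All adverse events will be reported on a standardized form". Collection is therefore not limited to attributed events.
- Study Timeline: the adverse events row is marked at placement, at 24-48 hours and on the day of removal, but not in the post-removal column.
- Background: of common stent symptoms, "they can occur in up to 80% of stented patients". The sentence describes occurrence in stented patients and states no attribution rule.

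**The concern.** A comparison of two event rates is interpretable only if both sides count the same thing. Here the study side is restricted, on the plain wording, to events judged to come from the stent. The published side may be restricted in the same way, or it may count every event in stented patients, and the protocol does not say which.

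Attribution is also a matter of judgement in this population. Participants have stones or strictures, and some have ureteroscopy in the same session. Several expected adverse events could equally be put down to the stone or the procedure. The judgement is made without stated criteria, in a study whose endpoint text already expects no events from the device design.

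At stake is a safety statement that could show the device as better than existing stents when the only difference is in what was counted. The protocol says the study is meant to inform a later powered trial, so a distorted rate could be carried into its planning.

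**Working it through.** The protocol gives no benchmark rate, safety margin, test or attribution share, so there is no figure of its own to reproduce. The calculations below show only how large the effect could be.

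**1. Size of the shift against an all-cause published rate.**

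Inputs, both assumed: the true all-cause rate of an event is 30% for this stent and for others, and 50% to 90% of the study's events are attributed to the stent.

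Counted rate = all-cause rate × share attributed.

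- 0.30 × 0.90 = 27%, an apparent advantage of 30 − 27 = 3 points.
- 0.30 × 0.50 = 15%, an apparent advantage of 30 − 15 = 15 points.

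If the published rate is restricted by the same attribution rule, both sides shrink together and the restriction alone creates no difference.

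**2. How often this could mislead at the planned size.**

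Inputs: n = 20 and n = 30, the enrolment range in Number of Research Participants; the Background's upper figure of 80%, used here only as a convenient all-cause rate; assumed attribution shares; and an exact one-sided binomial test at 0.025, which the protocol does not specify. A result is called lower than 80% if at most 11 of 20, or at most 18 of 30, participants have an event. The true all-cause rate is set at 80%, so every such result is false.

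| Share attributed | Counted rate | False result, n = 20 | False result, n = 30 |
|---|---|---|---|
| 100% | 80% | 1.0% | 0.9% |
| 90% | 72% | 8% | 11% |
| 80% | 64% | 27% | 39% |
| 70% | 56% | 55% | 73% |
| 50% | 40% | 94% | 99% |

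The first row is the position when all events are counted.

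**3. The FDA comparator.**

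For equal true rates, the ratio of the study rate to the FDA rate = share attributed in the study ÷ share of events that reach the FDA. Take 80% attributed and an assumed range of reporting completeness:

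- 100% reported: 0.8 / 1.00 = 0.8
- 50% reported: 0.8 / 0.50 = 1.6
- 25% reported: 0.8 / 0.25 = 3.2
- 10% reported: 0.8 / 0.10 = 8

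This comparison favours the device only if reporting is nearly complete, and otherwise runs against it. The protocol gives no figure for completeness, so the direction cannot be settled.

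**The case against.** The strongest reply is that the attribution wording is loose rather than a deliberate restriction. The endpoint lists relationship to device among the things to be assessed, and all adverse events go on the form, so a sensible analyst could tabulate both all events and related events. Symptoms are also captured by the symptom questionnaire and the pain score with no attribution step. That is fair as to data capture: nothing is lost. It does not settle the endpoint, whose plain wording summarises attributed events. An analysis plan that follows it inherits the restriction.

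The size of the effect is also open to challenge. The 30% rate and the attribution shares are assumptions. At 20 to 30 participants, 3 points is 0.6 to 0.9 of a participant. Exact 95% intervals around 30% run from 12% to 54% (6 of 20) and from 15% to 49% (9 of 30). The protocol sets no test or threshold, so the harm is to a descriptive comparison. All of this stands and limits the weight of the point.

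A reader might infer more than the protocol supports in four ways:

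- **That the comparison is biased in the device's favour outright.** This holds only where the published rate is all-cause, which the protocol does not say. The FDA comparison may run the other way.
- **That the 80% figure is the benchmark.** It is a Background remark about symptoms and is not named as a comparator.
- **That unmasked staff are assigned to make the attribution.** This is a reasonable inference, since nobody outside the study team is described, but the protocol never says who decides causality.
- **That relationship to device becomes constant once events are restricted.** It could still be graded, for example from possible to definite.

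**Conclusion.** The point holds as a conditional one. The primary safety endpoint restricts the study's side of an external comparison by an attribution judgement that has no stated criteria or independent check, and it does not require the published side to match. Where a published rate is all-cause, the comparison leans toward the device: by 3 to 15 points if the true rate is 30% and 50-90% of events are attributed, both assumptions. Where the published rate is attributed by the same rule, the restriction alone introduces no bias. For FDA reportable events the direction is unknown. Because no formal test or decision rule depends on the comparison, this is a weakness in a descriptive safety statement that is worth correcting, and not a threat to the study's conduct.

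**What to change.** Reword the primary safety endpoint, and the matching objective, so that:

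- The primary safety summary is the incidence of all adverse events from stent insertion through stent removal, by severity and regardless of attribution. This is the window in which the Study Timeline schedules adverse event collection. Running it to the last contact would go beyond that schedule.
- The stent-attributed subset is shown second.
- Each summary is compared only with published rates that use the same definition: all events with all-cause rates, attributed events with attributed rates. Using the all-event rate in every comparison would create the opposite mismatch against device-attributed published rates.
- The comparison with FDA reportable events is presented as descriptive context only.

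The cost is endpoint wording and one more table, from events the protocol already collects. The headline rate may look less favourable. This is a cheap improvement.

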- Dysuria
- Urethral discomfort
- Incontinence

- Hematuria
- Stent migration
- Stent encrustation
- UTI
- Bacteriuria
- Signs of ureter trauma
- Additional stent specific procedures

Risks to Research Participants

There is a potential risk of loss of confidentiality of your data. Every effort will be made to keep the patients' information confidential.

The study participants may feel uncomfortable while addressing some of the questions in the pain questionnaire. They may refuse to answer any of these questions. They may stop their participation in this study at any time.

Ureteral stents are as a SoC procedure that is reported in the literature to be associated with adverse events including: • Flank pain/loin discomfort • Flank pain when voiding • Suprapubic pain/lower abdominal pain • Trigonal irritation • Urinary frequency • Nocturia • Urinary urgency • Dysuria • Urethral discomfort • Incontinence • Hematuria • Stent migration • Stent encrustation • UTI • Bacteriuria • Signs of ureter trauma • Additional stent specific procedures

In case any patient experiences any unexpected adverse events, the study team will hold study recruitment until the investigation is completed. Patients who experience unanticipated adverse events will have the RELIEF stent promptly removed.

Provisions to Protect the Privacy Interests of Research Participants

The study subjects will be reviewed in a private room or space and will be protected against viewing by any person either not on the study team or not currently caring directly for the subject. There will be no discussion outside closed doors regarding any information pertaining to data collected.

Potential Benefit to Research Participants

We assume that the potential benefits from participating in this study may include little to no backflow of urine to the kidney, less flank pain and less bladder irritative symptoms than the current standard of care. However, given that the stent is under investigation, these benefits cannot be guaranteed.

Withdrawal of Research Participants

Study participants will remain in the trial unless they choose to withdraw or they no longer meet the inclusion or exclusion criteria. Participants will be free to withdraw at any part of the study period without any influence on their treatment pathway or care.

Alternatives to Participation

If a patient chooses not to participate in this study, standard of care treatment will be provided.

Costs to Research Participants

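### One of the two comparators in the primary safety endpoint is not like-for-like: stent-attributed events with no severity cut-off are set against FDA reportable events per US placement

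*Protocol*

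**What the plan says.** Under Study Endpoints, the primary safety endpoint is the assessment of stent-attributed adverse events by incidence, relationship to the device and severity. Two references are named: rates from published clinical studies, and "FDA reportable event occurrences, compared to number of US annual ureteral stent placements". The Objectives section carries the same comparator among the secondary objectives ("FDA reportable event occurrences, compared to number of US annual ureteral stent"). Neither place gives an FDA count, a number of placements, a resulting ratio or a definition of reportable.

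On what the trial will count:

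- The endpoint itself notes that "known complications from stenting may be observed".
- The list headed "Expected Adverse Events include" contains frequency, nocturia, urgency, dysuria, urethral discomfort, incontinence, hematuria, and flank and suprapubic pain, alongside migration, encrustation and UTI.
- Risks to Research Participants repeats that list as what stenting is "reported in the literature to be associated with adverse events including".
- The data and safety monitoring section states: "Subjects will be asked to report any adverse events to the study coordinator or physician". All events go on a standardized form that records tests, therapies and clinical visits.

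The Background says of the common stent symptoms that "they can occur in up to 80% of stented patients". Study Design gives "Intervention Model: Single Group Assignment", so there is no concurrent control.

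**The concern.** A comparison of rates can be read only if both numerators count the same kind of event. Here one side takes in every stent-attributed event, including symptoms that are common with any stent. The other takes in only events that meet a reporting criterion. Ascertainment differs too: each trial patient is asked directly, while the FDA figure depends on reports set against national placements.

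Both differences push the same way. They raise the trial figure relative to the FDA ratio, so a stent that behaved exactly like a traditional one could look worse on this comparator. With a single group, outside references are the only context for the safety result, and this is one of the two that the endpoint names. What is at stake is how the primary safety result is described. No test, margin or decision rule hangs on it.

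**Working it through.** The protocol states no benchmark, margin or expected rate for this comparison, so there is no figure of its own to reproduce. The check is a comparison of definitions, followed by an illustration.

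**1. The two sides**

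| | Trial side | FDA side |
|---|---|---|
| Events counted | Stent-attributed, no severity or seriousness cut-off | Reportable events only |
| How found | Patients asked for any adverse event | Reports, set against national placements |
| Denominator | 20 to 30 enrolled patients | US annual stent placements |
| Figure given | None | None |

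The absence of a cut-off is inferred from three things: severity is recorded but not used as a filter, patients are asked for any adverse event, and the expected list contains low-grade symptoms. That the FDA class is narrower rests on the plain meaning of reportable.

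**2. Does the 80% figure concern listed events?** The Background names eight common symptoms: urgency, frequency, dysuria, incontinence, hematuria, suprapubic discomfort, fever due to urinary tract infection, and flank pain. Seven correspond directly to entries on the expected-event list. The eighth is covered by UTI. So the symptoms behind the 80% ceiling would count as trial events when attributed to the stent.

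**3. What the trial might show.** Exact (Clopper-Pearson) two-sided 95% limits for x patients with an event out of n are the 2.5% quantile of Beta(x, n−x+1) and the 97.5% quantile of Beta(x+1, n−x).

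| Patients with a listed event | n = 20 | n = 30 |
|---|---|---|
| 80% (Background ceiling) | 16/20, 56.3% to 94.3% | 24/30, 61.4% to 92.3% |
| 20% (assumed) | 4/20, 5.7% to 43.7% | 6/30, 7.7% to 38.6% |

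**4. Against an assumed FDA ratio.** The ratio is not in the documents. Over an assumed 0.1%, 1% and 5% per placement, the quotient (trial rate ÷ benchmark) is:

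- at 80%: 80/0.1 = 800, 80/1 = 80, 80/5 = 16;
- at 20%: 20/0.1 = 200, 20/1 = 20, 20/5 = 4.

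Even in the 20% case the lower limits (5.7% and 7.7%) lie above all three assumed benchmarks. The direction is stable over this range. The size is not known, because both inputs to each quotient are a ceiling or an assumption.

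**5. If the event classes were matched.** This step concerns only how a repaired comparison should be labelled; it is not part of the defect. With zero reportable-type events, the two-sided 95% upper limit is 1 − 0.025^(1/n): 1 − 0.025^(1/20) = 16.8%, or 1 − 0.025^(1/30) = 11.6%. A count of zero could not show agreement with a rare-event rate.

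**The case against.** The strongest reply is that this belongs in the SAP, which is not at hand. Deciding which trial events are set against which reference is ordinary SAP content. The endpoint also collects severity and relationship, which is what a class-by-class comparison would need. On a generous reading, published rates serve the common symptoms and FDA occurrences serve the reportable events.

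Part of this stands. The endpoint never says that events of every severity will be pooled against the FDA ratio, and a matched subset might be formed from the planned data. But the comparator is written into the protocol endpoint in two places, one undivided set of trial events is set against both references, and nothing in the protocol pairs event classes with references. That is a choice stated badly, not a detail left open.

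The reply is also right that the documents give no FDA figure and that 80% is an upper bound from the Background. A reader might infer that any excess over the FDA ratio would be produced by definition and not by the device. The documents do not support that: without the ratio or a definition of reportable, an excess could come from either or both. Nor should one infer that the whole safety endpoint is uninterpretable. The published-rate reference may well be like-for-like, and nothing here counts against it.

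**Conclusion.** The point holds for the FDA comparator alone. As written, it sets a broad, solicited event count against a narrower class of reported events, so an apparent excess could arise from definition and ascertainment alone. This rests on the trial count being unrestricted, which the endpoint wording, the monitoring section and the expected-event list all indicate, and on reportable meaning fewer than all adverse events.

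The size of the mismatch cannot be stated. The quotients of 4 to 800 above depend on assumed benchmarks and on trial rates of 20% (assumed) to 80% (a ceiling), and none of them is a prediction for this trial. The published-rate comparator, the 48-hour success criterion and the planned 20 to 30 patients are unaffected. Severity: minor.

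**What to change.** Amend one phrase in two places, the primary safety endpoint and the matching secondary objective. Either:

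- drop the FDA-per-placement ratio and rely on the published-study rates already named; or
- keep it, limit it to trial events that meet a stated reportable-event definition, and label it descriptive context only. Reporting methods would still differ, and 20 to 30 patients cannot confirm agreement with a rare-event rate.

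The cost is small: one external benchmark is given up or narrowed. Dropping it needs no data. Limiting it would draw on the severity assessment and on the therapies and visits already recorded for each event. Whether those items suffice to classify events can be confirmed only once the definition is chosen.
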